#### 2.1.4.1 Adverse events variables

Adverse events (including SAEs, AESI and product complaints) are recorded from the time of signed informed consent to the end of the study. All AEs diagnosed by the Investigator will be reported and described.

All AEs will be coded to a "Lowest Level Term (LLT)", "Preferred Term (PT)", "High Level Term (HLT)", "High Level Group Term (HLGT)", and associated primary "System Organ Class (SOC)" using the version of MedDRA currently in effect at Sanofi at the time of database lock.

## Adverse event observation period

- Pre-treatment AEs are AEs that developed or worsened or became serious during the pre-treatment period.
- Treatment-emergent AEs are AEs that developed or worsened or became serious during the TEAE period.
- Post-treatment AEs are AEs that developed or worsened or became serious during the post-treatment period.

### Adverse events of special interest

An AESI is an AE (serious or non-serious) that needs to be monitored, documented, and managed in a pre-specified manner described in the protocol.

For this study, the AESI are:

- Increase in alanine aminotransferase (ALT):
  - o ALT  $\geq$  3 times the upper limit of normal range (ULN) (if baseline ALT  $\leq$ ULN) or ALT  $\geq$  2 times the baseline value (if baseline ALT  $\geq$ ULN);
- Allergic drug reactions:
  - o requiring consultation with another physician AND selected using the standardized MedDRA query (SMQ) "hypersensitivity" (broad and narrow) excluding the following PTs linked to local injection site reactions {"injection (infusion) site dermatitis", "injection (infusion) site hypersensitivity", "injection (infusion) site

- oedema", "injection (infusion) site rash", "injection (infusion) site urticaria", "injection (infusion) site eczema", "injection (infusion) site vasculitis", "injection (infusion) site swelling"};
- o in addition, an analysis will be performed for any general allergic event not meeting AESI criteria (not requiring consultation with another physician) but meeting the above SMQ criteria.

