# • Local injection site reactions:

- o deemed to be allergic by the Investigator (or have an allergic component) AND that require consultation with another physician AND related to alirocumab (as opposed to another injectable) AND selected using the following selection of PTs from the safety complementary form for local injection site reaction or from the reported term {"Injection (infusion) site dermatitis", "Injection (infusion) site hypersensitivity", "Injection (infusion) site oedema", "Injection (infusion) site rash", "Injection (infusion) site urticaria", "Injection (infusion) site eczema", "Injection (infusion) site vasculitis", "Injection (infusion) site swelling"};
- o in addition, an analysis will be performed for any local injection site reaction not meeting AESI criteria (not allergic and not requiring consultation with another physician) but meeting the above criteria AND related to alirocumab (as opposed to another injectable).
- Pregnancy of female patient (including male patient's partner) selected using appropriate MedDRA codes.
- Symptomatic overdose with alirocumab:
  - an overdose with alirocumab is defined as at least twice of the intended dose within the intended therapeutic interval (i.e., 2 or more injections are administered in <7 calendar days), to be reported using the term "symptomatic OVERDOSE" (accidental or intentional), indicating the circumstance in parentheses (e.g., "symptomatic overdose [accidental]" or "symptomatic overdose [intentional]"). These events will be selected using the AESI category as selected by the site.
  - in addition, another analysis will be performed analysing all overdose cases (whether symptomatic or asymptomatic) related to alirocumab using the HLT for overdose.

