# • Neurologic events:

- o requiring additional exams/procedures or consultation AND selected using SMQ "demyelination" (broad and narrow), "peripheral neuropathy" (broad and narrow), and "Guillain Barre syndrome" (broad and narrow) excluding the following PTs "acute respiratory distress syndrome", "asthenia", "respiratory arrest", and "respiratory failure";
- o an additional analysis will be performed analyzing all events meeting the above SMQ criteria for neurologic events whether or not the criteria for an AESI are met (whether or not requiring additional exams/procedures or consultation).
- Any neurocognitive events:

26-Apr-2017

- o selected using the company CMQ based on HLGTs "Deliria (incl confusion)", "Cognitive and attention disorders and disturbances", "Dementia and amnestic conditions", "Disturbances in thinking and perception", "Mental impairment disorders";
- o in a second approach, neurocognitive events will be analyzed as per the CMQ developed using the FDA grouping of events based on PTs "Amnesia", "Amnestic disorder", "Anterograde Amnesia", "Behavioural and Psychiatric Symptoms of Dementia", "Change in sustained attention", "Cognitive Disorder", "Confusional State", "Delirium", "Dementia", "Dementia Alzheimer's type", "Dementia with Lewy Bodies", "Disorientation", "Disturbance in attention", "Executive dysfunction", "Frontotemporal Dementia", "Illogical Thinking", "Impaired reasoning", "Incoherent", "Judgement impaired", "Memory Impairment", "Mental Impairment", "Mental Status Changes", "Mini Mental Status Examination Abnormal", "Presenile Dementia", "Retrograde Amnesia", "Senile Dementia", "Thinking Abnormal", "Transient Global Amnesia ", "Vascular Dementia" and the LLTs "Mental State Abnormal Aggravated", "Thinking Slowed";
- o in a third approach, neurocognitive events will be analysed using company CMQ or FDA CMQ.

Analyses of allergic drug reactions and local injection sites reactions and neurologic events will also be provided using the drop-down on the e-CRF AE page as a second approach.

All analyses described above as additional are not AESI, but AE groupings that will be explored.

In addition the following grouping of events will be provided:

- Hepatic disorder events using SMQ "Hepatic disorder";

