#### Analysis of all treatment-emergent adverse events

The following TEAEs summaries will be generated for the safety population.

- Overview of TEAEs, summarizing number (%) of patients with any
  - o TEAE;
  - Serious TEAE;

- o TEAE leading to death;
- TEAE leading to permanent treatment discontinuation (patients in usual care treatment arm with no additional LMT are excluded from denominator).
- Number (%) of patients experiencing TEAEs by primary SOC, HLGT, HLT, and PT sorted by the international agreed SOC order and by alphabetical order for the other levels (HLGT, HLT, PT);
- Number (%) of patients experiencing common TEAE(s) presented by primary SOC, HLT and PT (HLT incidence ≥2 % in any treatment group), sorted by internationally agreed SOC order and by alphabetic order for the other levels (HLT and PT);
- Number (%) of patients experiencing TEAEs by primary SOC and PT, sorted by the internationally agreed SOC order and by decreasing incidence of PTs within each SOC (in the alirocumab group). This sorting order will be applied to all other tables of TEAEs by SOC and PT, unless otherwise specified;
- All TEAEs regardless of relationship in one column and, in the same table a second column with TEAEs related to IMP according to Investigator's opinion by primary SOC, HLGT, HLT and PT;
- All TEAEs by maximal intensity (i.e., mild, moderate or severe), presented by primary SOC and PT, sorted by the sorting order defined above;
- The event rate per patient-year (the number of patients with an event in question divided by total patient-years) will be provided for all TEAEs by SOC and PT. For a patient with event, patient year is censored at time of first event; for patient without event, it corresponds to length of TEAE period;
- Kaplan-Meier curves will be provided, when appropriate, for time from first dose of openlabel IMP to the first occurrence of selected TEAEs as well as incidence rates at the time of analysis (Week 24 for the first analysis, Week 32 for the final analysis). Hazard ratio versus usual care group and corresponding 95% CI will be given. Patients without any event will be censored at the end of the TEAE period. Selected TEAEs will be local injection site reactions, general allergic reactions, neurocognitive events, hepatic disorders and TEAE related to any clinically significant signal that needs further characterization.

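### The SAP splits SMQ-selected general allergic events by whether consultation was required, specifies no SMQ total, and does not say which events enter the allergic-reaction hazard ratio

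*SAP*

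**What the plan says.** SAP Section 2.1.4.1 (Adverse events of special interest) selects the allergic AESI by two conditions together: the event needed consultation with another physician, and its term falls in the hypersensitivity SMQ (broad and narrow), apart from listed injection-site terms. It then adds an analysis of "any general allergic event not meeting AESI criteria (not requiring consultation with another physician) but meeting the above SMQ criteria".

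Other event types in the same section are handled differently. For neurologic events the additional analysis is described as "analyzing all events meeting the above SMQ criteria for neurologic events whether or not the criteria for an AESI are met". For overdose it takes every case, symptomatic or not.

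Three further outputs concern allergic events:

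- Section 2.1.4.1 says that analyses of allergic drug reactions, among others, "will also be provided using the drop-down on the e-CRF AE page as a second approach".
- Section 2.4.5.1 tabulates all TEAEs by arm down to preferred term, with event rates per patient-year by SOC and PT.
- Section 2.4.5.1 plans Kaplan-Meier curves and incidence rates: "Selected TEAEs will be local injection site reactions, general allergic reactions, neurocognitive events, hepatic disorders", plus any event tied to a signal. For these, "Hazard ratio versus usual care group and corresponding 95% CI will be given".

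Protocol Section 10.4.1.3 leaves the need for consultation to the investigator's medical judgment. SAP Section 1.1 states that the study is open-label.

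**The concern.** The variable that divides allergic events into two tables is a decision taken after the event by someone who knows the treatment. If investigators refer more readily on alirocumab, the AESI comparison moves against alirocumab and the non-AESI comparison moves in its favour, even when the arms have the same number of patients with allergic events. A total over both parts would not be affected by that split, but the SAP does not specify one for the SMQ grouping.

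The protocol introduction reports rare and sometimes serious allergic reactions with alirocumab, so this is a comparison that readers will look for. General allergic reactions are also one of four named event types that receive a hazard ratio. If its event set is left open, the programmer's choice among three candidate sets could decide which side of 1 the estimate falls.

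**Working it through.** **1. The sets side by side (SAP 2.1.4.1)**

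| Event type | AESI set | Additional analysis | Relation to AESI set |
|---|---|---|---|
| General allergic | SMQ and consultation | SMQ and no consultation | Complement |
| Neurologic | SMQs and further examination or consultation | All SMQ events | Contains it (union) |
| Overdose | Symptomatic | All cases, by HLT | All cases |

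Only the allergic row lacks an all-cases analysis.

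**2. Why the two tables do not add up**

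Tables count patients once per group. For each arm,

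N(total) = N(AESI) + N(non-AESI) − N(both).

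N(both) is not reported. The tables therefore only bound the total between the larger count and the sum. For example, 17 and 11 patients are compatible with any total from 17 to 17 + 11 = 28.

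**3. How referral alone moves the two parts**

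There is no figure in the plan to reproduce. The inputs below are assumptions: the same total incidence p in both arms, referral share rA on alirocumab and rU on usual care, and one event per patient.

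- AESI incidence = p × r, so the ratio between arms is rA / rU.
- Non-AESI incidence = p × (1 − r), so the ratio is (1 − rA) / (1 − rU).
- Total incidence = p in each arm, so the ratio is 1.00.

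p cancels, so the ratios do not depend on the incidence assumed.

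| rA vs rU | AESI ratio | Non-AESI ratio | Total ratio |
|---|---|---|---|
| 30% vs 30% | 1.00 | 1.00 | 1.00 |
| 40% vs 30% | 1.33 | 0.86 | 1.00 |
| 50% vs 30% | 1.67 | 0.71 | 1.00 |
| 60% vs 30% | 2.00 | 0.57 | 1.00 |
| 60% vs 20% | 3.00 | 0.50 | 1.00 |

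In planned arm sizes (280 and 140, SAP 1.1), with p = 10% and referral 60% vs 30%:

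- AESI: 280 × 0.06 = 16.8 vs 140 × 0.03 = 4.2 patients.
- Non-AESI: 280 × 0.04 = 11.2 vs 140 × 0.07 = 9.8 patients.
- Total: 28 vs 14 patients, which is 10% in each arm.

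These expected counts are small, so any observed ratio would also be imprecise.

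**4. Which set enters the hazard ratio**

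Section 2.4.5.1 attaches no consultation condition to general allergic reactions, which suggests the total. The same section says groupings are analysed with the Section 2.1.4.1 selections, which offer the AESI set, its complement, or the drop-down approach, whose categories are not defined. The nearest phrase in Section 2.1.4.1, general allergic event, appears in the definition of the non-consultation set. Protocol Section 10.6.2.2 uses general allergic reactions as a wider category that includes acute injection reactions. The AESI set, its complement and the union can each be defended from the text.

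**The case against.** A reader might infer that allergic events are reported only in these two parts, that every arm comparison therefore follows referral habits, and that no total allergic incidence will be produced. The documents do not support this. The drop-down approach is a further allergic analysis. The all-TEAE tables show each hypersensitivity term by arm whatever the consultation status. The Kaplan-Meier analysis may turn out to be a total. What stands is narrower: none of these is defined as the SMQ total. The preferred-term tables do not give a patient-level union, and the contents of the other two are not stated.

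Referral is also not wholly discretionary. The criterion is that consultation is required. Protocol Section 10.6.2.1 directs obviously allergic cutaneous events to a dermatologist, without restriction by arm. Nor are the instructions confined to alirocumab: Section 10.6.2 speaks of IMP, and the added usual-care drugs are IMP. This limits the scope for differential referral in that class of event but does not remove it elsewhere.

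It would also be too much to say that the union is free of bias. A dermatologist's report can lead to a corrected AE form, which may change the coded term and so its SMQ membership. Knowledge of the arm can also affect whether a mild event is reported at all. The total ratio of 1.00 above is an idealisation.

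Finally, the stakes are limited. Protocol Section 11.4.3 rules out formal inferential testing of safety, SAP Section 2.4.5 calls the summaries descriptive, and Section 2.1.4.1 presents the additional groupings as exploratory. The AESI subset itself follows the protocol definition. All of this stands and lowers the priority, but a hazard ratio with a confidence interval will still be read as a comparison.

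**Conclusion.** The point holds in a limited form. The additional allergic analysis is written as the complement of the AESI set, so no SMQ total regardless of consultation is specified and none can be derived by adding the two tables. The split rests at least partly on the judgment of an investigator who knows the arm. The event set for the hazard ratio of general allergic reactions is ambiguous.

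The size of any distortion cannot be determined from the documents, which give neither a referral rate nor an expected allergic incidence for this trial. Over the assumed referral shares shown, the AESI ratio runs from 1.00 to 3.00 and the non-AESI ratio from 1.00 down to 0.50, with no true difference. These figures show the mechanism and are not a forecast; with equal referral shares the distortion disappears. The change is worth making at modest priority.

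**What to change.** 1. In SAP Section 2.1.4.1, redefine the additional allergic analysis as all TEAEs meeting the stated SMQ criteria, with the same injection-site exclusions, whether or not consultation was required. This mirrors the rule already used for neurologic events.
2. In Section 2.4.5.1, state that this combined set is used for the Kaplan-Meier curve, incidence rates and hazard ratio of general allergic reactions.
3. Keep the AESI subset as a separate row.

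The cost is a sentence in each of the two sections and one derived flag in the adverse event dataset. No new data are needed, because the two sets already planned require both the SMQ selection and the consultation status. The change removes the split by referral; it does not remove other open-label reporting bias.

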# • Local injection site reactions:

- o deemed to be allergic by the Investigator (or have an allergic component) AND that require consultation with another physician AND related to alirocumab (as opposed to another injectable) AND selected using the following selection of PTs from the safety complementary form for local injection site reaction or from the reported term {"Injection (infusion) site dermatitis", "Injection (infusion) site hypersensitivity", "Injection (infusion) site oedema", "Injection (infusion) site rash", "Injection (infusion) site urticaria", "Injection (infusion) site eczema", "Injection (infusion) site vasculitis", "Injection (infusion) site swelling"};
- o in addition, an analysis will be performed for any local injection site reaction not meeting AESI criteria (not allergic and not requiring consultation with another physician) but meeting the above criteria AND related to alirocumab (as opposed to another injectable).
- Pregnancy of female patient (including male patient's partner) selected using appropriate MedDRA codes.
- Symptomatic overdose with alirocumab:
  - an overdose with alirocumab is defined as at least twice of the intended dose within the intended therapeutic interval (i.e., 2 or more injections are administered in <7 calendar days), to be reported using the term "symptomatic OVERDOSE" (accidental or intentional), indicating the circumstance in parentheses (e.g., "symptomatic overdose [accidental]" or "symptomatic overdose [intentional]"). These events will be selected using the AESI category as selected by the site.
  - in addition, another analysis will be performed analysing all overdose cases (whether symptomatic or asymptomatic) related to alirocumab using the HLT for overdose.

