#### • Pregnancy:

- Pregnancy occurring in a female patient or the partner of a male patient (if permitted by the female partner and by local regulatory authorities) during the study or within 70 days following the last dose of study drug (open-label alirocumab) or 70 days following the last dose of usual care treatment (IMP) (as applicable) or Day 225, whichever comes first. If the patient is randomized to usual care and the Investigator has not prescribed an additional LMT, the "date of the last dose of study drug" is defined as the date of the last on-site study visit.
- Pregnancy will be recorded as AESI in all cases. Pregnancy will be qualified as an SAE only if it fulfils one or more SAE criteria.
- In the event of pregnancy of a female patient included in the study, study product should be discontinued.
- The follow-up of the pregnancy will be mandatory until the outcome has been determined.
- Symptomatic overdose with alirocumab:
  - An overdose (accidental or intentional) is an event suspected by the Investigator or spontaneously notified by the patient (not based on systematic injection counts) and defined as at least twice of the intended dose within the intended therapeutic interval (ie, 2 or more injections are administered in <7 calendar days), to be reported using the Term "symptomatic OVERDOSE" (accidental or intentional), indicating the circumstance in parentheses (eg, "symptomatic overdose [accidental]" or "symptomatic overdose [intentional]"). The patient should be monitored and appropriate symptomatic treatment instituted.
  - The circumstances of the overdose should be clearly specified in the verbatim and symptoms entered on separate AE/SAE forms.
  - Of note, asymptomatic overdose should be reported as a standard AE.
- Other project specific AESI(s)
- Allergic events (including local injection site reactions that are allergic in nature):

- Allergic drug reactions and/or local injection site reactions deemed to be allergic by the Investigator (or have an allergic component), that require consultation with another physician for further evaluation of hypersensitivity/allergy as per the Investigator's medical judgment should be reported as an AESI.

Note: Other local injection site reactions are non-AESIs. Please see Section 10.4.1.4 for details.

- Neurologic events:

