## 10.4.1.4 Local injection site reactions

Local injection site reactions that are considered non-allergic (eg, local injection site reactions related to mechanics of injection) or allergic but not requiring consultation with another physician are not considered as AESIs but should be reported as standard AEs.

Local injection site reactions that are considered by the Investigator as non-allergic events and that are related to the alirocumab injection, as opposed to another injectable agent, should be further characterized by evaluating the related symptoms that comprise an injection site reaction such as but not limited to redness, pain, etc.

Under certain circumstances, no AE of local injection site reactions should be reported as this is not typically considered a clinically important finding:

- The patient has erythema/redness, and/or swelling, and all <2.5 cm, AND
- The swelling does not interferes with activity, AND
- No other signs or symptoms are involved.

Note: if the patient has a reaction of swelling with a diameter <2.5 cm that interferes with activity, it should be considered as a clinically relevant finding and should be reported as an AE with a corresponding intensity of moderate or severe, in accordance with Appendix G.

The definition of local injection site reactions, the reporting time frame, and the corresponding complementary forms in the e-CRF to be filled are summarized in Appendix D.

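### The SAP's bracketed definition of non-AESI local injection site reactions contradicts its own lead phrase and the protocol: 'and' should be 'or'

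*SAP*

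**What the plan says.** SAP 2.1.4.1, under local injection site reactions, defines the AESI by joining conditions. The reaction must be "deemed to be allergic by the Investigator (or have an allergic component) AND that require consultation with another physician AND related to alirocumab" rather than to another injectable, and it must carry one of eight listed injection-site PTs.

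The next bullet adds a second analysis. Its lead phrase is "any local injection site reaction not meeting AESI criteria". A bracket then explains the phrase as "not allergic and not requiring consultation with another physician", and the sentence ends "but meeting the above criteria AND related to alirocumab (as opposed to another injectable").

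The protocol draws the line differently. Section 10.4.1.4 treats as standard adverse events those reactions that are non-allergic, "or allergic but not requiring consultation with another physician are not considered as AESIs but should be reported as standard AEs". Section 10.4.1.3 adds a residual rule after defining the allergic AESI: "Other local injection site reactions are non-AESIs".

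For general allergic events, SAP 2.1.4.1 writes the companion analysis without this problem: "any general allergic event not meeting AESI criteria (not requiring consultation with another physician) but meeting the above SMQ criteria". One clinical condition is negated and the retained selection is named.

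**The concern.** The bracket negates each of two conditions separately and then requires both negations. A rule that needs two features together fails as soon as either one is absent, so the bracket does not describe the reactions that fail the AESI rule. It describes only those that lack both features.

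The SAP therefore gives two incompatible selection rules in one sentence, and two programmers could follow it in good faith and produce different counts for the alirocumab arm. One of the categories at risk, allergic reactions without consultation, is one that the protocol expressly names as non-AESI. SAP 1.5 and 1.6 record no departure from the protocol, so nothing suggests that the narrower rule was intended.

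The closing condition has a related weakness. It does not say which of the criteria above are to be kept. The AESI bullet above it contains the allergic and consultation conditions as well as the PT list.

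**Working it through.** The plan states no figure here, so the check is one of logic. Restrict attention to reactions that are related to alirocumab and carry a listed PT, since both bullets appear to keep those two conditions. Let A = allergic (or with an allergic component) and C = required consultation with another physician.

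Rules as written:

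- AESI (SAP 2.1.4.1): A and C.
- Companion analysis, lead phrase (SAP 2.1.4.1): not (A and C), which equals (not A) or (not C).
- Companion analysis, bracket (SAP 2.1.4.1): (not A) and (not C).
- Non-AESI under Protocol 10.4.1.4: (not A) or (A and not C). This reduces to (not A) or (not C), the same as the lead phrase.

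| Allergic | Consultation | AESI | Companion, by bracket | Companion, by lead phrase | Protocol non-AESI |
|---|---|---|---|---|---|
| yes | yes | yes | no | no | no |
| yes | no | no | **no** | yes | yes |
| no | yes | no | **no** | yes | yes |
| no | no | no | yes | yes | yes |

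Counting combinations that belong to neither SAP grouping:

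- By the bracket: 4 − 1 (AESI) − 1 (companion) = 2 unassigned.
- By the lead phrase: 4 − 1 − 3 = 0 unassigned.
- By the protocol: 4 − 1 − 3 = 0 unassigned, with both mixed rows classed as non-AESI.

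The protocol agrees with the lead phrase in every row and disagrees with the bracket in the two mixed rows. The allergic, no-consultation row is named in Protocol 10.4.1.4. The non-allergic, consultation row follows because that section classes non-allergic reactions as non-AESI without regard to consultation, and because the residual rule in 10.4.1.3 covers whatever is left.

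Now the closing condition. If the criteria above meant every condition in the AESI bullet, an event would have to satisfy (A and C) while failing it, and the grouping would be empty under either reading. That cannot be meant. Read with the parallel bullet for general allergic events, which names the SMQ selection, the intended meaning is the PT selection. With that meaning and 'or' in the bracket, the companion grouping covers 3 rows and the AESI covers 1: no gap and no overlap.

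**The case against.** The best defence is that the lead phrase governs. It already takes in every reaction that fails the AESI rule, including both mixed rows, and the bracket is a loose gloss on it. The protocol supports that reading. This much stands: the SAP does not unambiguously require both negations, and the defect is a sentence that contradicts itself. But a gloss that states a narrower rule is still a rule that someone may program.

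The second defence is that other outputs cover the same events. SAP 2.4.5.1 tabulates all treatment-emergent events by system organ class and PT whatever their AESI status. It also plans detailed tables for treatment-emergent local injection site reactions, without expressly limiting them to AESIs. SAP 2.1.4.1 plans a second approach based on the e-CRF drop-down and says that the additional analyses are exploratory groupings, not AESIs. This stands too, and it sets the limit on the consequence. It does not settle which rule the PT-based grouping uses. SAP 2.4.5.1 refers back to 2.1.4.1 for its selections, and whether the drop-down captures a given event depends on how the site coded it.

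A reader might go further than the documents allow in three ways:

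- **That these reactions are lost and the reported incidence is too low.** They remain in the tables of all treatment-emergent events, and the plan nowhere says that the two groupings are to be summed to give total incidence.
- **That the number affected can be estimated.** Protocol section 4 gives 6.2% for local injection site reactions under alirocumab, and 0.062 × 280 = 17.4 patients. But that is a pooled rate for such reactions generally, not for this eight-term list, and nothing in the documents says what share would fall in the mixed rows.
- **That the PT list is part of the error because it has no term for redness or pain.** How wide the list should be is a separate choice of scope. The logical fault exists whatever terms are on it.

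**Conclusion.** The point holds as an internal contradiction in SAP 2.1.4.1 and a conflict with Protocol 10.4.1.3 and 10.4.1.4. The stated selection rule in the bracket is wrong as the complement of the AESI rule. This is more than missing detail.

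Its size is 2 of 4 combinations unassigned if the bracket is coded literally, and 0 of 4 if the lead phrase is coded. The practical effect is possible under-counting in one exploratory, descriptive PT-based grouping. No primary or secondary efficacy result is touched, and no event disappears from safety reporting.

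Two assumptions underlie this: that the closing condition means the PT selection, as the parallel bullet suggests, and that the relatedness condition applies to both groupings, as the text says. No number of patients can be derived from the documents.

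**What to change.** In the companion bullet for local injection site reactions in SAP 2.1.4.1:

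- Change the bracket to read *not allergic or not requiring consultation with another physician*.
- Replace the open reference to the criteria above with *meeting the above PT selection*, in line with the wording already used for general allergic events, and keep the relatedness condition.

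The AESI and companion groupings then divide all alirocumab-related local injection site reactions within the selected terms, and match the protocol. It would also help to state in SAP 2.4.5.1 which set the local injection site reaction tables and Kaplan-Meier curves use.

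The cost is a wording change to the SAP and the matching line of programming. No new data are needed, and no clinical or reporting rule for sites changes.
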